1.2. Rationale

Non-communicable diseases that are rapidly developing among HIV-positive with stable ART, including cardiovascular disease. Atorvastatin administration supposed to have a positive effect on the reduction of subclinical atherosclerosis assessed by the thickness of the carotid artery intima media. The use of atorvastatin, a cheap and widely accessible drug in Indonesia, has not been specifically studied in term of improving cardiovascular disorder in HIV-infected patients under ART.

2. OBJECTIVES

2.1. Primary Objective

To compare the effect of 48 weeks of 20 mg daily atorvastatin versus placebo on changes CIMT in virally suppressed HIV patients with CMV seropositivity

2.2. Secondary Objective

1. To evaluate the interaction between baseline CMV copy number and effect of atorvastatin on CIMT changes
2. To evaluate the effect of 48 weeks of 20 mg daily atorvastatin versus placebo on fasted lipid changes in virally suppressed HIV patients with CMV seropositivity
3. To evaluate the effect of 48 weeks of 20 mg daily atorvastatin versus placebo on of brachial artery flow mediated vasodilatation (FMD) in virally suppressed HIV patients with CMV seropositivity
4. To evaluate the effect of 48 weeks of 20 mg daily atorvastatin versus placebo on liver fibrosis and steatosis changes in virally suppressed HIV patients with CMV seropositivity
5. To evaluate the effect of 48 weeks of 20 mg daily atorvastatin versus placebo on neurocognitive changes in virally suppressed HIV patients with CMV seropositivity
6. To evaluate the effect of 48 weeks of 20 mg daily atorvastatin versus placebo on several immune activation biomarkers (sCD14, VCAM, ICAM, hsCRP, and β 2M) changes in virally suppressed HIV patients with CMV seropositivity
7. To evaluate the effect of 48 weeks of 20 mg daily atorvastatin versus placebo on oral periodontitis score changes in virally suppressed HIV patients with CMV seropositivity
8. To evaluate the interaction between baseline CMV copy number and effect of atorvastatin on FMD, neurocognitive function, liver fibrosis and steatosis, lipid profile, and immune activation biomarkers changes in 48 weeks

3. STUDY ENDPOINTS

3.1. Primary endpoint

The mean or median CIMT changes of virally suppressed HIV patients with CMV seropositivity in atorvastatin group versus placebo group between baseline and week 48

3.2. Secondary endpoints

1. Magnitude of change in effect of atorvastatin on CIMT associated with baseline CMV copy number
2. The mean or median changes of fasted lipid between baseline and week 24, week 24 and week 48

3. The mean or median changes of brachial artery flow mediated vasodilatation (FMD) between baseline and week 48
4. The mean or median changes of liver fibrosis and steatosis in atorvastatin and placebo group between baseline and week 48
5. The mean or median changes of sCD14, VCAM, ICAM, CRP, and β 2M in atorvastatin and placebo group lipid between baseline and week 24, week 24 and week 48
6. The mean or median changes of neurocognitive function in atorvastatin and placebo group lipid between baseline and week 24, week 24 and week 48
7. The mean or median changes of oral periodontitis score in atorvastatin and placebo group between baseline and week 48
8. Magnitude of change in effect of atorvastatin on FMD, neurocognitive function, liver fibrosis and steatosis, lipid profile, and immune activation biomarkers associated with baseline CMV copy number

[figure not shown]

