	
medication.
 
7. At week 24, blood collection procedures and neurocognitive examination procedures will be repeated.
 
8. At week 48, blood collection procedures, CIMT, FMD, transient elastography with CAP, neurocognitive examination, and community periodontal index procedures will be repeated.

Study Duration	
The study will be conducted from April, 2019 to April, 2021. Predicted accrual period: 4 months Enrollment of the first study participant to enrollment of last participant schedule on four months in the first year.

Primary Endpoint(s)	
The mean or median CIMT changes of virally suppressed HIV patients with CMV seropositivity in atorvastatin group versus placebo group between baseline and week 48

Secondary endpoints	
 - Magnitude of change in effect of atorvastatin on CIMT associated with baseline CMV copy number - The mean or median changes of fasted lipid between baseline and week 24, week 24 and week 48 - The mean or median changes of brachial artery flow mediated vasodilatation (FMD) between baseline and week 48 - The mean or median changes of liver fibrosis and steatosis in atorvastatin and placebo group between baseline and week 48 - The mean or median changes of sCD14, VCAM, ICAM, CRP, and β2M in atorvastatin and placebo group lipid between baseline and week 24, week 24 and week 48 - The mean or median changes of neurocognitive function in atorvastatin and placebo group lipid between baseline and week 24, week 24 and week 48 - The mean or median changes of oral periodontitis score in atorvastatin and placebo group between baseline and week 48 - Magnitude of change in effect of atorvastatin on FMD, neurocognitive function, liver fibrosis and steatosis, lipid profile, and immune activation biomarkers associated with baseline CMV copy number

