6.2.2. Analysis of secondary endpoints

- Linear regression with interaction will be used to assess magnitude of change in effect of atorvastatin on CIMT associated with baseline CMV copy number
- For other continuous endpoints, a 2 sample T-test

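### The lipid, neurocognition and biomarker endpoints omit the baseline-to-week-48 change that their objectives point to, and the endpoint 8 interactions have neither a window nor a usable test

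*Combined protocol and SAP*

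**What the plan says.** Section 2.2 words objectives 2 to 7 on one template. Objective 2 reads "To evaluate the effect of 48 weeks of 20 mg daily atorvastatin versus placebo on fasted lipid changes", and objectives 5 and 6 follow it for neurocognition and for sCD14, VCAM, ICAM, hsCRP and β2M. Objective 8, on interaction with baseline CMV copy number, ends with "lipid profile, and immune activation biomarkers changes in 48 weeks".

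In section 3.2, repeated in the synopsis, the lipid endpoint is "The mean or median changes of fasted lipid between baseline and week 24, week 24 and week 48". The neurocognition endpoint is "The mean or median changes of neurocognitive function in atorvastatin and placebo group lipid between baseline and week 24, week 24 and week 48", and the biomarker endpoint has the same two windows. Other endpoints span the whole period: the primary endpoint in section 3.1 is "in atorvastatin group versus placebo group between baseline and week 48", and the FMD endpoint is "changes of brachial artery flow mediated vasodilatation (FMD) between baseline and week 48".

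Endpoint 8 begins "Magnitude of change in effect of atorvastatin on FMD, neurocognitive function, liver fibrosis and steatosis, lipid profile" and continues to the biomarkers and baseline CMV copy number without naming a time window.

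Section 6.2.2 assigns a regression with an interaction term to the CIMT question. Its only other line is "For other continuous endpoints, a 2 sample T-test".

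**The concern.** The question asked and the comparison listed do not line up for three groups of outcomes. If the aim is the effect of the full treatment period, the comparison that answers it is the between-arm difference in change from baseline to week 48. That contrast is not listed, so the analyst would have to decide, possibly with data in hand, whether to add it and how to weigh it against the two interval results.

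Endpoint 8 has a separate gap. Neither its window nor a method capable of estimating it is stated for any outcome other than CIMT.

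**Working it through.** **1. Windows side by side** (objectives from section 2.2, endpoints from section 3.2; weeks)

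| Objective | Outcome | Endpoint | Window named |
|---|---|---|---|
| 3 | FMD | 3 | 0–48 |
| 4 | Liver fibrosis, steatosis | 4 | 0–48 |
| 7 | Periodontal score | 7 | 0–48 |
| 2 | Lipids | 2 | 0–24 and 24–48 |
| 5 | Neurocognition | 6 | 0–24 and 24–48 |
| 6 | Five biomarkers | 5 | 0–24 and 24–48 |
| 8 | CMV interaction, outcomes other than CIMT | 8 | none |

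Six objectives share a template. Three have 0–48 endpoints and three do not.

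**2. Does another section supply the window?** No. Sections 6.2 to 6.2.3 give none for these outcomes. Appendix B defines change variables only for CIMT, FMD, liver fibrosis and steatosis.

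**3. Can the 48-week result be read off the two interval tests?** Let d1 be the between-arm difference in mean change over weeks 0–24, d2 the same over weeks 24–48, and d the same over weeks 0–48.

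- In participants with all three visits, d = d1 + d2. In differing sets of participants this need not hold, and medians, which the endpoints allow, do not add.
- Var(d) = Var(d1) + Var(d2) + 2 Cov(d1, d2). The separate t-tests supply the first two terms only. The week-24 value enters the first change with a plus sign and the second with a minus sign, so the covariance is not in general zero.

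The point estimate can therefore sometimes be recovered, but the standard error and p-value cannot.

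**4. Can the listed test estimate endpoint 8?** The quantity sought is b3 in

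change = b0 + b1·arm + b2·CMV + b3·(arm × CMV) + error.

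A two-sample t-test compares arm means and contains no CMV term, so it returns no estimate of b3. As for the window, FMD and liver measures are taken only at baseline and week 48, so only one change exists. Lipids, neurocognition and biomarkers also have a week-24 value, so three windows are possible and none is named.

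**5. Are the data there?** Yes. Appendix A schedules lipids at screening, week 24 and week 48, and neurocognition and stored samples at randomization, week 24 and week 48. Section 4.13.2 collects CMV DNA at baseline.

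**6. Is the sample size touched?** No. The stated figure is for CIMT: 0.1/0.12 = 0.833; a two-sample t-test at 90% power and 5% (taken as two-sided) needs 31.25, rounded up to 32 per arm; 32/(1 − 0.20) = 40. It reproduces and does not involve these endpoints.

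**The case against.** In objectives 2, 5 and 6, 48 weeks is the length of treatment, not a measurement window. Two consecutive intervals do cover those 48 weeks, and only objective 8 attaches the period to the changes themselves. The endpoint wording is also loose (a stray reference to lipids appears in the biomarker and neurocognition endpoints), so the list may be shorthand for three visits. An analyst wanting the 48-week result would simply subtract baseline from week 48.

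This stands in part. It means the 48-week target is an inference, though a strong one given the parallel objectives and objective 8. It does not supply the missing contrast: a later week-48-minus-baseline analysis would be sensible but not prespecified.

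For endpoint 8, its wording parallels that of the CIMT interaction endpoint, so the same regression was plausibly intended. That is fair, but section 6.2.2 does not say it.

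Three stronger readings are tempting and not supported:

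- **That endpoint 8 contradicts objective 8 by naming the two sub-intervals.** It names no interval; its window is unstated, not conflicting.
- **That the plan rules out a 48-week comparison.** It omits one; nothing prohibits it.
- **That the interval wording costs power, or misstates precision or error rates by a definite amount.** Such a figure would need effect patterns and between-visit correlations that the documents do not give. It would also need a rule for combining the intervals or declaring success on them, and the plan states none.

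**Conclusion.** The point holds as a minor one. Three secondary endpoints, covering lipids, neurocognition and five biomarkers, lack the baseline-to-week-48 contrast that best answers their objectives, and no planned test provides it. This rests on reading objectives 2, 5 and 6 in the same way as 3, 4 and 7. The endpoint 8 gap is separate and does not depend on that reading: the window is unstated, and outside CIMT the only listed method cannot estimate the interaction. No numerical size is attached, because the documents give no effect size, standard deviation or correlation for these outcomes. The primary endpoint and the 40 per arm are unaffected.

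**What to change.** - **Synopsis and section 3.2, endpoints 2, 5 and 6:** add the change from baseline to week 48, with the screening value as baseline for lipids. Identify it as the contrast that answers the objective, tested with the two-sample t-test already planned. Keep the 0–24 and 24–48 changes as additional contrasts.
- **Synopsis and section 3.2, endpoint 8:** state baseline to week 48 as the window.
- **Section 6.2.2:** extend the linear regression with an arm-by-baseline-CMV interaction, now given for CIMT only, to the baseline-to-week-48 change of each endpoint 8 outcome.

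The cost is wording. No visit, sample or participant is added. The downside is one more contrast per unpowered secondary outcome; for the five biomarkers, 5 × 2 = 10 arm comparisons become 5 × 3 = 15. Saying which contrast answers the objective keeps that addition interpretable.

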4. STUDY BENEFIT

4.1. Potential Benefit(s)

There are some potential benefits to those individuals who use atorvastatin such as lowering lipid level, but this will not be available for those who got placebo. However, society will gain general knowledge that will improve care of similar cases.

METHODS

4.2. Study Plan

4.3. Study Design

This study used a double-blind randomized placebo-controlled trial design. Participants who met the inclusion and exclusion criteria were randomized into atorvastatin groups and placebo groups with a ratio of 1: 1 (40 subjects per group). Randomization using a computer program based on randomization of permutation blocks with block 4 sizes carried out by statistical analysts. Then the code is given to pharmacists who involved in the study. Researchers, doctors, and participants did not know the results of randomization.

4.4. Study Sites and Duration

The study will conduct during 2019-2020 at HIV Integrated Care Unit and Integrated Cardiovascular Care Cipto Mangunkusumo Hospital, Jakarta.

4.5. Population and Sample Size

Target population is HIV-positive patient on stable ART routinely controlled in HIV Integrated Care Unit Cipto Mangunkusumo Hospital, Jakarta.

Assuming that the effect size is 0.1, standard deviation is 0.12, and the use of 2 sample t-test, the sample size needed for 90% power and 5% significant level is 32 per arm. With additional 20% drop, each arm (placebo and control group) will need 40 participants.

4.6. Eligibility Criteria

4.6.1. Inclusion Criteria

1. Age between 20 to 45 years old
2. Using stable ART at least 1 year
3. positive CMV IgG
4. Viral load HIV RNA <50 copies / ml

4.6.2. Exclusion Criteria

1. Undergoing for Hepatitis C DAA Therapy
2. Decompensated cirrhosis or acute liver failure
3. History of coronary artery disease
4. Diabetes mellitus
5. History of of brain infection, epilepsy, stroke
6. History of rhabdomyolysis or myopathy
7. Pregnant or breastfeeding
8. Severe depression
9. Using statin therapy in the past 6 weeks
10. History of statin hypersensitivity
11. *Framingham Risk Score* above 10% within LDL \geq 130
12. *Framingham Risk Score* under 10% within LDL \geq 160
13. Out of Periodontitis Index (Upper right molars, top series, upper left molars, lower right molars, bottom series, lower left molars)

4.6.3 Drop Out Criteria

1. Pregnant during this study
2. Stop using ART > 1 month
3. Stop or refuse to use atorvastatin during this study
4. Not willing to continue as participant in this study

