	
10. History of statin hypersensitivity
 
11. Framingham Risk Score above 10% within LDL \geq130
 
12. Framingham Risk Score under 10% within LDL \geq160
 
13. Out of Periodontitis Index (Upper right molars, top series, upper left molars, lower right molars, bottom series, lower left molars)
 
Drop out criteria:
 
 1. Becomes pregnant during this study 2. Stop using ART > 1 month 3. Stop or refuse to continue to use atorvastatin during this study 4. Not willing to continue as participant in this study
Participating sites	HIV Integrated Care Unit, Tertiary Hospital Cipto Mangunkusumo
Study Design	This study using double blind randomized, placebo-controlled clinical trial. Subject chosen by consecutive methods.
Study Scheme or Intervention	Eligible subjects will be randomized to receive an atorvastatin or placebo with a ratio of 1: 1. Atorvastatin 20 mg or identical placebo capsules will be given orally for 48 weeks.
Schedule of Procedures/ Evaluations	
 1. The participants who meet the inclusion and exclusion criterias (except viral load, anti-CMV, and Framingham score criterias) get an explanation of the purpose, method of the study, the rights to stop or refuse to take part during in the study. And each participant gives their sign to ICF. 2. Viral load, IgG anti-CMV, fasted lipid profile, fasting glucose and insuline to define Framingham score will be done as screening process. 3. Participants with CMV seropositivity, undetectable viral load, and Framingham risk score $>$10% LDL $<$130 or Framingham risk score $<$10% LDL $<$160 will continue the study process. 4. Participants will be asked to fast for 10 hours before taking 12 mL of venous blood: for examination of blood glucose, ALT, CMV DNA, and sCD14, VCAM, ICAM, hsCRP, β2M, and transient elastography with CAP. CIMT, FMD, neurocognitive examination, and Community Periodontal Index will be done within a week before taking study drugs. 5. Participants will be randomized to get atorvastatin therapy or placebo. While using study drugs, participants continue their ART and other standard of cares. 6. Study drugs will be dispensed monthly along with ART refill and the pharmacist records the remaining

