4.10. Participant Retention

To enhance participant retention, all participant will be monitored by research assistant using phone once every two weeks. In addition, a reminder of the next schedule visit will be sent a week before.

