6.2.3 Missing data plan

We will compare subject characteristics in the drop out with remaining participants. If there is no different of the characteristic, we assume that the missing is at random.

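### Stopping study drug counts as drop-out without a stated consequence; if it is applied as leaving the study, the only follow-up CIMT is lost and the as-randomised analysis is put at risk

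*Combined protocol and SAP*

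**What the plan says.** Section 4.6.3 gives four drop-out criteria. Item 3 is "Stop or refuse to use atorvastatin during this study"; the synopsis has almost the same words, "Stop or refuse to continue to use atorvastatin during this study". Item 4 is "Not willing to continue as participant in this study". Someone who stops tablets but is happy to keep attending therefore meets item 3 and not item 4. Item 2, "Stop using ART > 1 month", is likewise about a drug and not about willingness to take part. Neither list says what happens once a criterion is met.

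Two sections use the term in a way that suggests outcomes are lost. Section 4.5 states: "With additional 20% drop, each arm (placebo and control group) will need 40 participants". Section 6.2.3 states: "We will compare subject characteristics in the drop out with remaining participants", and then: "If there is no different of the characteristic, we assume that the missing is at random". It names no imputation or model.

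Other sections point the other way:
- 4.10: "all participant will be monitored by research assistant using phone once every two weeks".
- 4.13 follows every participant for a year from starting study drug.
- 4.13.3 and Appendix A schedule the week-48 CIMT with no exception for people off drug.
- 6.2 analyses participants in their randomised group whatever treatment they received.
- 8.1 frames its safety evaluation as a decision on stopping the study drug and says nothing of leaving the study.
- 9.6 names stopping treatment and stopping participation as separate things, and has interruptions of either kind recorded on the CRF.

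**The concern.** The as-randomised analysis in 6.2 needs a week-48 CIMT from people who stopped their tablets. Appendix A shows CIMT at randomisation and at week 48 only, so no interim value can stand in, and a missed scan cannot be recovered later. The primary analysis in 6.2.1 is a t-test on change and uses only people who have both scans.

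If staff read item 3 as ending participation, stoppers leave the primary analysis. The trial then compares people who stayed on their tablets, which is a different quantity from the one 6.2 describes. Stopping may also be related to arm, since drug stops under 8.1 could fall under item 3. Staff cannot tell from the text which reading applies.

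**Working it through.** **The plan's own figure.** Inputs from 4.5: effect 0.1, SD 0.12, two-sample t-test, 90% power, 5% level. Section 4.5 gives no unit, and I read mm from Appendix B. It gives no sidedness either; two-sided reproduces the stated figure.
- At 32 per arm, SE = 0.12 × √(2/32) = 0.030 and the noncentrality is 0.10/0.030 = 3.33. Noncentral-t power is 0.907; at 31 per arm it is 0.898. So 32 is reproduced.
- 32/(1 − 0.20) = 40, also reproduced.
- The allowance is 8 of 40 per arm, for all drop-out reasons together. It protects the number measured and assumes the full 0.1 effect in those who remain.

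**Effect estimated if stoppers are removed.** Assume a share p = 20% stops in each arm and active-arm stoppers gain nothing.
- Completers: 0.10 mm.
- As randomised: (1 − 0.20) × 0.10 + 0.20 × 0 = 0.08 mm.
- Gap: 0.02 mm, although stopping is equal in the two arms.

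**Type I error if stoppers are removed and there is no treatment effect.** Let stoppers have a mean CIMT change worse by d than completers in the same arm. Then bias = p_active × d_active − p_placebo × d_placebo, which is (p_active − p_placebo) × d when d is common. It is zero when both the rates and the prognosis of stoppers match. The figures below are from the noncentral t at SD 0.12, with completers out of 40 per arm. All values of p and d are assumptions.

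| Stopping, active v placebo | n analysed | d = 0.03 mm | d = 0.06 mm | d = 0.12 mm |
|---|---|---|---|---|
| 20% v 20% | 32 v 32 | 5.0% | 5.0% | 5.0% |
| 20% v 15% | 32 v 34 | 5.0% | 5.1% | 5.5% |
| 10% v 5% | 36 v 38 | 5.0% | 5.1% | 5.5% |
| 20% v 10% | 32 v 36 | 5.1% | 5.5% | 6.9% |
| 10% v 0% | 36 v 40 | 5.1% | 5.5% | 7.1% |
| 20% v 0% | 32 v 40 | 5.5% | 7.0% | 13.2% |

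At 5-10 point imbalances and d up to 0.06 mm, the bias is 0.0015 to 0.006 mm. The last cell has bias 0.20 × 0.12 = 0.024 mm; it needs stopping in one arm only and a deficit of a full SD, which exceeds the planned effect. If more people stop on placebo, the sign reverses.

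**Power if stoppers are kept.** Assume 20% of the active arm stop with no benefit, so the effect is 0.08 mm. The active-arm SD is √(0.12² + 0.20 × 0.80 × 0.10²) = 0.1265. With 40 v 40 measured, SE = √(0.1265²/40 + 0.12²/40) = 0.0276, noncentrality 2.90, power 0.818.

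**The case against.** The best reply is that the plan already keeps stoppers in. Sections 4.13, 4.13.3 and Appendix A carry no exception for people off drug, 6.2 sets treatment received aside, and 9.6 separates treatment from participation. The 20% in 4.5 proves little, because criteria 1, 2 and 4 can also cause losses. That leaves 6.2.3 as the main support for the leave-the-study reading, and it does not mention item 3.

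Much of this stands. A reader might infer that the protocol removes stoppers, or that the analysis in 6.2 cannot be carried out. The documents do not establish either. Section 6.2 settles the group in which a person is analysed, and missing outcomes are a separate matter that a prespecified method could address under assumptions. But none of the sections cited says that someone meeting item 3 keeps the week-48 scan, and 6.2.3 uses the same term for people whose data are missing. The conflict remains.

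A reader might also infer from the word atorvastatin that the rule applies to one arm only. It is probably loose wording for study drug: 4.12.2 masks participants, doctors, researchers and outcome assessors. Masking does not prove this, because 4.11.2 has tablets given by staff who know the treatment. The text should simply name both arms.

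Finally, most of the type I error figures show little harm. That is correct, and the point does not rest on them.

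**Conclusion.** The point holds as a conflict between sections that bears on the primary endpoint. Item 3 makes stopping the drug a drop-out reason distinct from withdrawal, 6.2.3 treats drop-outs as missing, and other sections fit continued follow-up. If item 3 is applied as removal, the primary t-test becomes a completer analysis and the as-randomised analysis in 6.2 is put at risk.

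The size is conditional, because the documents give no stopping rate, imbalance or prognosis for stoppers. The 0.02 mm gap assumes 20% stopping with no benefit in active-arm stoppers. A reader might suppose that equal stopping makes the completer analysis safe; that protects type I error (given equal prognosis) but not the size of the estimate. A reader might equally infer serious inflation of type I error; that appears only under extreme assumptions. It should be fixed because the fix is cheap and a missed scan is irrecoverable, not because large bias has been shown. Confidence is medium.

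**What to change.** - Define drop-out, and reconcile 4.6.3 and the synopsis with 4.10, 4.13, 4.13.3, 6.2, 6.2.3, 8.1 and 9.6.
- Reword item 3 as stopping study drug in either arm, distinct from withdrawal from the study.
- State that participants who stop study drug but remain willing keep the already scheduled week-24 and week-48 assessments, including the week-48 CIMT, and are analysed as randomised.
- State whether items 1 and 2 end follow-up or only treatment. Which it should be is for the sponsor, and nothing here changes when treatment is stopped.
- Record the date of and reason for stopping in the interruption record that 9.6 already requires, and tabulate by arm after unblinding. The CRF was not available to check, so these fields may already exist.

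The cost is a short amendment, at most two CRF fields, and no extra visits. The plan should acknowledge that power is lower if retained stoppers gain nothing: about 82% at 20% stopping with 40 v 40 measured. That loss follows from the as-randomised analysis already chosen in 6.2, not from the rewording.
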